### ***Sample size calculation***

Based upon the assumption that we need to reach 90% accuracy, in light of the results of Resnick CM et al (2016), the computed effect size for the accuracy of linear measurements was found to be (1.05), using alpha ( $\alpha$ ) level of (5%) and Beta ( $\beta$ ) level of (20%) i.e. power = 80%; the study will include 10 subjects. To compensate for 15% for the use of non-parametric tests; the final minimum estimated sample size will be 12 subjects. Sample size calculation was performed using G\*Power Version 3.1.9.2.

Patients to be included:

- a) Patients who have class III facial deformity to be corrected using bimaxillary orthognathic surgery.
- b) No medical problems that might interfere with general anesthesia or interfere with bone and soft tissue healing.

Patients will be excluded if:

- a) There are craniofacial anomalies including cleft lip/palate,
- b) Patient have previous maxillofacial operations or facial scars,
- c) Correction mandates multi-segment Le Fort I osteotomies,
- d) There are orthodontic appliances in place at the time of T1 records.
- e) Genioplasty is recommended for deformity correction.
- f) There is facial Asymmetry.

All the patients are consented for using their data in research purposes.

The CBCT scans of class III patients who undergone maxillary advancement with minimal or without impaction and mandibular setback will be identified. The preoperative and 6 months postoperative CBCT images will be anonymized and will be saved in a password protected computer. Only the research team members will have access to the research data.

In order to quantify the actual amount of surgical movement, the pre and post-operation CBCT voxel based super imposition using ONDEMAND 3d. The surgical movement will be quantified using direct slice land-marking.

Using the pre-operation CBCT to do the surgical mock up and the soft tissue simulation on dolphin 3D. Soft tissue surface models of the simulation and the actual postoperative images will be generated and exported as STLs.

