### **3D Virtual planning and prediction:**

The limitations of the Two-dimensional (2D) computer programs for cephalometric measurements and treatment prediction were widely used. Through the development of three-dimensional (3D) examination techniques and computerized analysis methods (Westermark et al. 2005) (20), the opportunity to make 3D computerized predictions of orthognathic treatments has arisen (Gateno et al. 2000, Gateno et al. 2003)(21,22) and authors started to compare the accuracy of both methods where the 3d virtual planning and prediction showed higher accuracy of the 3d than the 2d method. In 2017 Bengtsson et al conducted a prospective randomized blinded case controlled comparison study on Treatment outcome of orthognathic surgery comparing planning accuracy in computer-assisted two- and three dimensional planning techniques, the study showed a statistically significant difference between 3D and 2D prediction methods with an advantage for the 3D. There are several studies on accuracy of 3D planning techniques (Marchetti et al. 2006, Xia et al. 2007, Mazzoni et al. 2010, Tucker et al. 2010, Aboul-Hosn Centenero and Hernandez-Alfaro 2012, Zinser et al. 2012, Hsu et al. 2013)(23–29). The majority of these studies did not test the prediction only; they also assessed transference of planned movements to surgery (occlusal templates) (Xia et al. 2007, Tucker et al. 2010, Aboul-Hosn Centenero and Hernandez-Alfaro 2012, Zinser et al. 2012, Hsu et al. 2013)(24,26,28–30). Almost all of the comparable studies on 3D planning have set the level for linear success at <2 mm and showed high success rates (80%–100%) (Marchetti et al. 2006, Xia et al. 2007, Mazzoni et al. 2010, Tucker et al. 2010, Hsu et al.

2013)(23,24,26,29). Hsu et al (*Hsu et al. 2013*)(29) presented the largest number of studied subjects (n=65) and found a mean linear difference for the maxilla of 1.1 mm and for the mandible 1.0 mm so it stepped on the 2D limitations with proved higher accuracy.

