### ***Study Hypothesis***

There will be no difference between actual soft tissue results and Dolphin 3D software soft tissue prediction.

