### **Data Analysis**

Superimposition of the predicted and the post-operative STLs and conformation of the generic meshes will be performed. Using VR mesh software, the mesh will be segmented into pre-identified anatomical regions. The distance between the corresponding vertices will be displayed

as a colour scale in milli-meter and will be analyzed in the individual dimension of space (x, y and z) using in-house software developed for this purpose and each dimension will be displayed as a colour coded distance map. It will be generated to illustrate the magnitude and anatomical regions with prediction inaccuracies analysis. Using this software, the minimum, maximum, mean, standard deviation (SD), absolute maximum, absolute mean, and absolute SD of 90% of the points of each facial anatomical region will be measured.

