### ***Statistical analysis***

Numerical data will be explored for normality by checking the distribution of data and using tests of normality (Kolmogorov-Smirnov and Shapiro-Wilk tests). Data will be presented as mean, median, standard deviation (SD), minimum, maximum and 95% Confidence Interval (95% CI) for the mean values. For parametric data, paired t-test will be used to compare between actual soft tissue measurement and software measurement. For non-parametric data, Wilcoxon signed-rank test will be used to compare between actual soft tissue measurement and software measurement. Inter- and intra-examiner reliability will be assessed using Cronbach's alpha and Intra-Class Correlation coefficients.

The significance level will be set at  $P \leq 0.05$ . Statistical analysis will be performed with IBM® SPSS® Statistics Version 20 for Windows.

---

\* IBM Corporation, NY, USA.

\* SPSS, Inc., an IBM Company.

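### The sample size rests on an undefined 90% accuracy target, and with no error limit set, the planned tests of difference cannot show that the prediction is accurate

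*Combined protocol and SAP*

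**What the plan says.** The Aim section sets out to evaluate how accurately the software predicts facial soft tissue change. The Study Hypothesis section states: "There will be no difference between actual soft tissue results and Dolphin 3D software soft tissue prediction".

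The Sample size calculation section begins "Based upon the assumption that we need to reach 90% accuracy". Citing a 2016 study, it then reports that "the computed effect size for the accuracy of linear measurements was found to be (1.05"). This value is standardised; no mean difference, SD or figure in mm comes with it. Alpha of 5% and power of 80% lead to 10 patients. After a 15% allowance for non-parametric tests, "the final minimum estimated sample size will be 12 subjects". The section does not name the test.

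The Statistical analysis section says: "For parametric data, paired t-test will be used to compare between actual soft tissue measurement and software measurement". The Wilcoxon signed-rank test is the alternative, and significance is set at P ≤ 0.05. The section also plans the "95% Confidence Interval (95% CI) for the mean values", other descriptive statistics and reliability coefficients. It plans no analysis of a percentage or proportion.

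The Data Analysis section measures distances between corresponding vertices of the predicted and postoperative meshes, by region and by axis. Its list of summaries ends with "absolute SD of 90% of the points of each facial anatomical region will be measured". That 90% selects mesh points; it is not an accuracy criterion.

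The background section on 3D virtual planning says that comparable planning studies "have set the level for linear success at <2 mm", with success rates of 80% to 100%. The methods neither adopt nor reject that level.

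**The concern.** An accuracy study has to say what size of error counts as accurate. Here the one numerical target, 90%, cannot be evaluated: it is not said what must be 90% accurate, within what error, or counted over what unit. The hypothesis is one of no difference, and the only tests named are tests of difference. Such a test can reject that hypothesis, but a failure to reject does not support it.

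The result that agrees with the stated hypothesis is therefore P > 0.05, and a small study produces it easily. The better material for judging accuracy, absolute error in mm with confidence intervals, is already planned. Without a limit fixed in advance, though, almost any observed error could be called acceptable afterwards.

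**Working it through.** **Inputs.** Effect size 1.05, power 80%, base sample size 10, 15% inflation and final size 12, all from Sample size calculation; alpha 0.05 from there and from Statistical analysis. Sidedness is not stated; two-sided is assumed because it reproduces the plan's figure. The documents give no SD and no margin, so results are in SD units unless marked as an assumption.

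**1. The plan's own figure.** For a paired (or one-sample) t-test, power is P(|T| > t(0.975, n−1)), where T is noncentral t with n−1 degrees of freedom and noncentrality 1.05 × √n.
- n = 9: power 0.787
- n = 10: power 0.839, the first to reach 80%
- n = 12: power 0.911

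Inflation: 10 × 1.15 = 11.5, so 12. The arithmetic reproduces. A one-sided test would have given 8.

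A one-sample test against a fixed limit gives the same n, so the calculation alone does not identify the hypothesis tested. The reading as a test against zero difference comes from Statistical analysis, which names only comparisons of actual with software measurement, and from the absence of any limit in the methods.

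**2. How often P > 0.05 occurs with 12 patients** (one comparison, two-sided paired t-test, bias in SDs of the paired differences).
- Bias 0.5 SD: noncentrality 0.5 × √12 = 1.73, power 0.353, non-significant 64.7%
- Bias 0.8 SD: noncentrality 0.8 × √12 = 2.77, power 0.714, non-significant 28.6%
- Bias 1.05 SD: power 0.911, non-significant 8.9%
- Zero mean bias, with over- and under-prediction balancing across patients: non-significant about 95% by construction, whatever the size of the individual errors

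**3. Precision with 12 patients.** The 95% CI half-width is t(0.975, 11)/√12 = 2.201/3.464 = 0.635 SD of whichever error measure is analysed.

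**4. A rule that does address accuracy.** Conclude accuracy for a region if the upper limit of the two-sided 95% CI for mean absolute error lies below a fixed limit. With n = 12 and roughly normal errors, power is 80% when the true mean is 0.889 SD below the limit (SD of absolute error across patients).
- If that SD were 0.5, 1 or 1.5 mm (assumption), the required distance is 0.44, 0.89 or 1.33 mm.
- If the limit were 2 mm (illustration only), the true mean absolute error would have to be at most 1.56, 1.11 or 0.67 mm.

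**5. Skewness.** Absolute errors tend to be right-skewed. Simulated gamma errors with coefficients of variation of 0.3 and 0.5 give a false-pass rate at the limit of about 4% to 5%, against a nominal 2.5%, and power of about 76% to 77% at 0.889 SD.

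**6. The 90% target read as a proportion** (assumption: 90% of patients within some limit). Even 12 successes in 12 give an exact two-sided 95% lower bound of 0.025^(1/12) = 73.5%. On that reading, 12 patients can describe the proportion but cannot demonstrate 90%.

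**The case against.** The strongest reply is that the plan never says a non-significant test will be read as accuracy. It aims to evaluate accuracy, and it will report signed and absolute errors in mm, colour maps and confidence intervals. That is right. A reader might infer that the sponsor intends to claim accuracy from P > 0.05; the documents do not say so. What remains is narrower but real: the stated hypothesis points towards that reading, and nothing else in the plan provides a criterion.

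Second, the test behind the 10 patients is inferred. This stands as a caution: the cited study is not available here, and the calculation fits a test against a limit equally well.

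Third, the background sections warn that signed values cancel and understate error. A reader might take that as the plan condemning its own paired test. It is not: those sections describe points on a facial surface cancelling within one comparison, whereas the 95% figure concerns cancellation between patients. The points are related but distinct, and the plan does not define which measurement enters the paired test.

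Fourth, 0.5 SD might be clinically trivial. Without an SD this cannot be excluded: it would be 0.25 mm if the SD of the paired differences were 0.5 mm (assumption). The miss rates show what the test can detect, not that any particular error is important.

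Fifth, the background pairs the 2 mm level with success rates, so the 90% may have been meant as a success rate. That is plausible but nowhere stated.

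**Conclusion.** The concern holds. The 90% accuracy basis is undefined and unanalysed, its link to 1.05 is not shown, and no limit is set against which the planned absolute errors or confidence intervals can be read. As written, the plan can detect a systematic bias but cannot support its own hypothesis of no difference. With 12 patients, P > 0.05 has a probability of 65% at a true bias of 0.5 SD, 29% at 0.8 SD, and about 95% when errors balance across patients. These figures assume one comparison, approximate normality and a two-sided 5% test.

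Two stronger readings are not supported. One is that the sample size is miscalculated: it reproduces. The other is that 12 patients are too few: that depends on the ratio of the limit to the SD, and the documents give neither for this study. Confidence is high on the missing definition and limit, and lower on which test the sample size was built for.

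**What to change.** 1. **Sample size calculation.** Delete the 90% accuracy basis, or define it with a unit and a tolerance in mm and report it descriptively. Show how 1.05 was derived. State the precision that 12 patients give: a 95% CI half-width of about 0.64 SD.
2. **Statistical analysis.** Before predicted and postoperative meshes are compared, fix a justified limit in mm, the region or regions, and the measure (total distance or a named axis). Say whether the 2 mm level from the background applies to soft tissue here. Conclude that a region is accurately predicted only if the upper limit of the two-sided 95% CI for its mean absolute error lies below the limit.
3. **Paired tests.** Keep them as tests of systematic bias only, and state that P > 0.05 is not evidence of accuracy.
4. **Power statement.** For one region and 12 patients, give about 80% power if the true mean is 0.89 SD below the limit and errors are roughly normal. Add that power is about 76% to 77% with right-skewed errors, with a false-pass rate of about 4% to 5% rather than 2.5%, and lower if several regions must all pass. Say that the adequacy of 12 depends on the limit and the SD.

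Cost: no added patients and no new measurements, since the absolute regional errors and the CIs are already planned. The sponsor must justify a limit in advance, and the stated figures become less favourable than the present ones.

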### **Data Analysis**

Superimposition of the predicted and the post-operative STLs and conformation of the generic meshes will be performed. Using VR mesh software, the mesh will be segmented into pre-identified anatomical regions. The distance between the corresponding vertices will be displayed

as a colour scale in milli-meter and will be analyzed in the individual dimension of space (x, y and z) using in-house software developed for this purpose and each dimension will be displayed as a colour coded distance map. It will be generated to illustrate the magnitude and anatomical regions with prediction inaccuracies analysis. Using this software, the minimum, maximum, mean, standard deviation (SD), absolute maximum, absolute mean, and absolute SD of 90% of the points of each facial anatomical region will be measured.

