### **Analysis based on surface meshes**

#### Pre and post-operative image registration for comparison:

The analysis of 3D surface polygonal meshes is one method of assessing topographical and positional surface changes in 3D. To assess the accuracy of the software-derived prediction compared to the actual final soft tissue image, registration or superimposition of the two images is required. This can be achieved using two methods. The first involves maintaining the existing hard and soft tissue relationship of each of patient's prediction and actual images and then superimposing the hard tissues on the anterior cranial base. As the hard and soft tissue relationship is 'locked', following hard tissue alignment, the soft tissues will also be aligned relative to their hard tissue position. The distance between the two soft tissue surfaces can then be analyzed. The second option is to ignore the underlying hard tissue and use the forehead region of the soft tissue only to align the two images. The results may be different, especially if the patient has lost adipose tissue from around the upper face region; this will

be immediately apparent if the images are aligned on the skull but not if they are aligned on the soft tissue only. Alignment of the images relying on the soft tissue only may also be difficult as there is less surface topography for the images to reliably align on.

Following alignment of the images, the distance between the two surfaces can be determined. The current method is based on the distance between one point on one surface and the closest point to it on the second surface. Note that the measurement relies on the closest point, which may not necessarily be the corresponding anatomical point. Unless the surface meshes are identical, there will be some points on one mesh where the closest point on the second mesh is absent, but the algorithm finds an inappropriate point on the second mesh and produces a large incorrect reading. To overcome the effects of these ‘outliers’, some studies ‘filter-out’ the values by using the 95th and 90th percentiles.(50–52)

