## **Patients and Methods**

This will be a retrospective study to investigate the accuracy of Dolphin 3d software for the prediction of post-operative soft tissue changes following bimaxillary orthognathic surgery to correct class III jaw defects through combined maxillary advancement and mandibular setback. The study will employ the pre-existing CBCT images routinely captured for orthognathic surgery patients in Glasgow dental hospital and school. Then difference between the pre-operative soft tissue prediction and the 6-month postoperative results will be analyzed. The study will be conducted in Glasgow dental school and hospital using patients pre-existing data after the ethical approval.

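### Does leaving the alignment region unstated for the predicted and post-operative surfaces undermine the accuracy comparison?

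*Combined protocol and SAP*

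**What the plan says.** The scan-handling paragraphs, which sit after the eligibility list under the Sample size calculation heading, describe one registration: "In order to quantify the actual amount of surgical movement, the pre and post-operation CBCT voxel based super imposition using ONDEMAND 3d". Its stated purpose is to measure how far the jaws moved. The next paragraph says that the mock-up and simulation are done in Dolphin 3D on the pre-operative CBCT, and then: "Soft tissue surface models of the simulation and the actual postoperative images will be generated and exported as STLs".

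Data Analysis follows with "Superimposition of the predicted and the post-operative STLs and conformation of the generic meshes will be performed". Distances between corresponding vertices are then analysed along x, y and z and summarised by anatomical region, with both signed and absolute statistics. VR mesh is named for segmentation and in-house software for the distances. No software, region or frame is named for the superimposition.

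The background subsection on image registration (under Analysis based on surface meshes) describes two routes. One keeps bone and skin locked together, "superimposing the hard tissues on the anterior cranial base". The other is to "use the forehead region of the soft tissue only to align the two images". Of the choice between them it says "The results may be different, especially if the patient has lost adipose tissue from around the upper face region".

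Patients and Methods gives the comparison: "Then difference between the pre-operative soft tissue prediction and the 6-month postoperative results will be analyzed". The Study Hypothesis is "There will be no difference between actual soft tissue results and Dolphin 3D software soft tissue prediction".

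**The concern.** Every outcome in this study is a distance between two aligned surfaces, so the alignment sets the zero from which prediction error is measured. If forehead skin drives the alignment and its thickness changes between the scans, part of that change becomes apparent prediction error lower in the face. A small tilt grows with distance from the aligned area, and the test in Statistical analysis cannot separate either effect from a real software error.

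The background section itself warns of this. The compared surfaces come from a pre-operative scan and a scan six months after surgery, and no eligibility criterion limits weight change, so the case it warns about can arise. The registration that is described has another stated purpose and its own region is not given. The scans also already exist, so an unstated choice could in principle be made after the distances have been seen. At stake would be a false finding of inaccuracy, or a real inaccuracy that goes undetected.

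**Working it through.** **1. The plan's own figure.** The Sample size calculation gives effect size 1.05, alpha 5%, power 80%, 10 subjects, raised by 15% to 12. A two-sided paired t-test with noncentrality 1.05 × √n has power 0.787 at n = 9 and 0.839 at n = 10, so 10 is reproduced. Inflation gives 10 × 1.15 = 11.5 or 10 / 0.85 = 11.8, and both round up to 12. The alignment question does not touch this calculation.

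**2. What a systematic shift would do.** Two assumptions are needed that the document does not supply: that the paired t-test is run on the signed regional mean, and that alignment adds a shift with a non-zero average across patients. With n = 12 and 11 df, the critical t is 2.201. The test rejects once the mean difference reaches 2.201 / √12 = 0.635 SD. With noncentrality equal to shift × √12:

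| True error (SD) | Mean shift (SD) | Chance of P ≤ 0.05 |
|---|---|---|
| 0 | 0 | 5% |
| 0 | 0.25 | 12% |
| 0 | 0.5 | 35% |
| 0 | 1.0 | 88% |
| 1.05 | 0 | 91% |
| 1.05 | −0.5 (net 0.55) | 41% |

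**3. What a shift averaging zero would do.** It leaves the false-positive rate alone but adds variance. If it is independent of the other error, the effect size becomes 1.05 / √(1 + s²), where s is the SD of the shift in units of the original SD.
- s = 0.5: 1.05 / √1.25 = 0.939, power 0.841.
- s = 1.0: 1.05 / √2 = 0.742, power 0.649.
- Without the shift, power is 0.911.

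A shift near zero on average is therefore not harmless if it varies between patients.

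**4. Tilt.** Displacement is about L × tan(θ), with L assumed to be 80 to 120 mm from the alignment area to the chin and θ assumed to be 0.5 to 1 degree.
- 0.5 degree: 80 × 0.00873 = 0.70 mm to 120 × 0.00873 = 1.05 mm.
- 1 degree: 80 × 0.01746 = 1.40 mm to 120 × 0.01746 = 2.09 mm.

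The lips are nearer a forehead reference than the chin, so they would move less. For scale, the introduction reports under 2 mm as the usual success level in 3D planning studies.

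**5. Which reading the text supports.** The arithmetic shows that a poor alignment could matter. Whether the plan leads to one is settled by the text.
- The data are CBCT throughout, so bone is available with the skin.
- The simulation starts from the pre-operative CBCT, so bone and predicted skin come from the same scan.
- The only registration method named is voxel-based and links the pre- and post-operative scans.
- The background says that bone alignment makes upper-face fat loss visible at once, that skin alignment does not, and that skin alone offers less topography to align on.
- The same background notes that areas used for alignment can be left out of the accuracy regions.

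Together these point to alignment on unoperated bone. Nothing in the methods points to forehead skin.

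**The case for a change.** The strongest case for a change is that the bone-based reading is an inference. Data Analysis lists superimposition as a step performed on the exported STLs, separate from the CBCT registration. No sentence says that the exports keep the registered coordinates, the region of the voxel registration is itself unstated, and the x, y and z axes are undefined. The authors know that the choice can alter results and still do not record it. One sentence would settle it at almost no cost, before any distances are computed.

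As a description of the text, all of that stands. Recording the region and axes when the work is done would help anyone who wants to reproduce it.

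It does not show that the plan, followed sensibly, gives a wrong answer. The harmful case needs an analyst to choose the option whose weaknesses the document itself sets out, when a bone-based registration is already part of the work. It then needs forehead change that runs in one direction across 12 patients, for which the document gives no figure. It also needs the signed mean to be the tested quantity. The plan lists signed and absolute summaries without choosing, and its background warns that signed values cancel. A test of an absolute mean against zero would reject almost regardless of alignment, because that mean is positive by construction. The worry about choosing after seeing the distances applies to any retrospective imaging study; nothing here suggests it is intended.

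**Conclusion.** The superimposition step is under-described, and the document acknowledges that the choice of alignment can affect results. This is a gap in detail that competent analysts would fill in the same way: register on unoperated bone through the CBCT data, as the background favours and the planned voxel-based registration allows. No stated rule is wrong and the sample size is unaffected.

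The possible size is conditional. A false-positive rate of 12% to 88% requires an assumed systematic shift of 0.25 to 1.0 SD in a signed test variable. A loss of power from 0.911 to 0.841 or 0.649 requires an assumed shift that averages zero with SD 0.5 or 1.0. A displacement of about 0.7 to 2.1 mm requires an assumed tilt of 0.5 to 1 degree over 80 to 120 mm. None of these inputs comes from the document, and the forehead-shift scenarios arise only if the less natural reading is adopted. The conclusion rests on bone-based alignment being feasible, that is, on the scans capturing a suitable unoperated area; the document does not state their coverage. No change to the plan is called for.
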